In 2019, Tidewave R&D and SunHF began discussing the prospect of assessing the newly developed Tidewave turning mattress (Tidewave). The development of Tidewave is based on a systematic review on the role of repositioning in the prevention of pressure injury (2018)¹, in addition to a pressure test performed by the Norwegian Research Center² (NORCE 2018/19). Patients at SunHF are potential users of this turning mattress, and it are therefore important candidates to test the mattress with focus on the product's quality regarding functionality and pressure injury (PI) prevention. One of the patient groups that would potentially benefit from the matress is individuals with spinal cord injuries, which is also one of the main patients groups at the hospital. In the trial, Tidewave will be compared with the recommended CuroCell® 4 AD (CuroCell) mattress to investigate the quality of the product with in particular focus on individuals with spinal cord injury (SCI).

January 1st 2022

[name] og [name]

Introduction

Sunnaas Rehabilitation hospital delivers acute rehabilitation to patients suffering from newly acquired injuries related to the spinal cord, as well as to the muscular and skeletal structure. The acute rehabilitation takes place from the departments focusing on spinal cord injury sequelae (RMS), and the department of multi trauma, neurology and burns (MNB). Newly injured individuals are admitted from the acute care hospital as soon as they are ready and in a condition to start their multidisciplinary rehabilitation program. In 2019, 82 patients, with a mean age of 56 years, received their acute rehabilitation at one of these two facilities. The mean length of stay was 71 days. After the rehabilitation, 63 (77%) of the patients were discharged to home, 8 (10%) to other hospitals, 7 (8%) to private rehabilitation facilities and 4 (5%) to nursing homes³. Individuals with paralysis and individuals recovering after multiple trauma has increased risk of pressure injury (PI) development, compared to individuals not suffering such injuries or diseases⁴⁻⁶. This is due to lack of sensibility, reduced or lack of voluntary mobility and areas of the skin being exposed to unfavourable moisture from sweating and incontinency⁷⁻⁹. Individuals with PI are often hospitalized over increased time-periods and are exposed to an increased number of outpatient consultations related to PI treatment and follow-up¹⁰. PI causing infection can potentially expose patients to life-threatening conditions^{8,9}. PI can also cause increased pain, tension and sleep deprivation. PI prevalence assessments performed at RMS and MNB in 2019 indicated that a major portion of the hospitalized patients were at risk of having a PI, and that 29% of the examined population at the two departments had a PI. This finding confirmed the importance and value of risk reducing intervention. The assessment also elaborated that the PIs occurred at areas of the body that are exposed to pressure over time, whilst in a supine position, e.g. such hips, buttock and heels. A long-time supine position demands a need for manual turning and, thus a waking of the individual during the night if the mattress is a standard static version. On the other hand, dynamic air mattresses are widely in use today, focusing on a variation in pressure, and thus a reduced need of position change during the imbedded time lap. Even though these mattresses reduce the need for manual turning, they do not eliminate the problem for individuals who are not capable of managing the position change on their own, and some individuals require position change assistance every second hour. The European Pressure Ulcer Advisory Panel's (EPUAP) 2019 guidelines¹¹ recommend an average of position change every second to forth hour. Further, they advise individuals at risk of PI development to be positioned in a 30-degree sideways posture¹¹.

Dynamic air mattresses represent a variation of quality, related to pressure variation of the mattress to prevent PIs. This pressure variation is due to automatic air change offered by an automatic air pump system. However, the noise generated by the pump could disturb the sleep, causing a decrease in quality of life over time.

Technical information regarding the mattresses

The intervention mattress, **Tidewave**, is a dynamic air mattress which automatically turns the patient from side to side with a maximum angle of 30 degrees at each side, over the course of a maximum of 180 minutes. When inflated, the mattress shape and retains a cradle formation, which in favour of increasing comfort and safety for the patient. The cradle shape provides a 10% increase in pressure distribution, in comparison to traditional posture alteration. In addition, the mattress provides a pressure relief caused by the continuous movement of the individual. The mattress is designed to be comfortable, increase sleep quality and reduce the amount of manual position changes required from the nursing staff. The mattress has three variations of weight recommendations, ranging upwards to a maximum of 150 kilos. The mattress has been tested in nursing homes, in individuals' homes and hospitals. The Norwegian Medicines Agency (NO918491775/0941-55297) has approved the mattress, and the mattress conforms to the European Regulation 2017/745, with a risk class 1 as per rules in Annex VIII. The developer, Tidewave R&D, started mass production of the product in October 2020.

The control mattress, **CuroCell® 4 AD**, is a dynamic mattress providing pressure variation and in prevention and treatment of PIs, this can be utilized. The mattress is functional and provides satisfying comfort for the individual. The removable bedsheets are documented to have a high hygiene standard, and is designed to allow moisture to pass through, reducing the risk of moisture related injuries to the skin. The mattress offers a variety of attributes, such as a heel function that reduces strain on exposed/sensitive heels. Recommended weight ranges from 0 – 200 kg. The mattress is in Sunnaas Rehabilitation hospital currently used as first of choice mattress to individuals at risk of PI development.

Contamination procedures

The hospital has established and implemented cleaning and disinfection procedures in accordance with current national regulations. These procedures will be followed throughout the project. This is especially important in contamination-related situations.

The purpose of the study

To compare an intervention mattress and a regular care mattress in relation to occurrence of pressure-relief, experienced sleep comfort, pain and quality of life in the participants. Further, to examine resources needed to assist in position change of the participants, as well as physical strain for the nurses.

Troubleshooting

Compare the Tidewave turning mattress (intervention mattress) to the CuroCell® 4 AD (control mattress) in relation to;

- 1) Development of PI risk
- 2) Noise disturbance, pain, quality of life, quality of sleep, general bedrest comfort.
- 3) Functionality in terms of daily use, such as getting dressed and repositioning to and from the bed.
- 4) Resource use in staff members with focus on amount of required manual position changes during the day, as well as number of staff members required for each manual position change, and the level of physical exertion required from the hospital staff to perform the position changes.

Material and Methods

Research design

To conduct a prospective cross over testing, with ten participants from the group of patients at the two acute rehabilitation departments.

A feasibility study was in advance of the main trial completed. The results from the feasibility trial supported the choice of inclusion and exclusion criteria regarding safety in the participants while testing the mattresses. Acceptable pressure limits were set, based on the findings in the feasibility study, as well as evidence-based knowledge regarding level of pressure and risk of PI¹². The feasibility study was performed between May 4th to 7th 2021.

Based on the results from the feasibility study, relevant validated and custom-made questionnaires were chosen to get the needed information regarding the participants' experience being bed rested on the mattresses. Custom-made questionnaires regarding experienced strain, resource use and physical exertion in the group of staff members was

developed. As well as two semi-structured questionnaires, focusing on in-depth knowledge of the participants' and the staff members' experience with the mattresses, respectively.

Selection of participants

Three to four weeks after admission to the RMS or MNB departments, between September 2021 and December 2022, ten participants will be included in the study. Participants included in the trial will suffer from SCI, neurological disease with paralysis or multi trauma. All with the consequence of decreased self-dependency and mobility, and thus lack of independency in position change in bed. The selection of candidates will be by the project nurse, based on the inclusion criteria, and in accordance with the responsible physician at the department. The duration for each participant will be 14 days, seven days on each of the mattresses. The project nurse will contact potential participants in person, provide oral information about the study, hand out written project information, as well as an invitation to participate.

Power calculation

The sample size calculation is based on the Insomnia Severity Scale (ISS) validation study by Morin et al (2011)¹³. The hypothesis is that the sleep will improve when using the intervention mattress, as compared to the control mattress. However, the expectation is a low improvement, due to the low period of time the intervention mattress will be in use. Thus, the sample size calculation will be based on what is denoted a “slight improvement”, defined by Morin et.al. as an improvement on 4.6 points on the ISS scale¹³. Based on this effect, a power of 0.8 and a significance level of 0.05, will need eight participants, given the set assumptions regarding variation (SD = 4.5, taken from Morin et. al). Thus, we include 10 participants to tolerate some drop- outs.

Inclusion criteria

- ≥ 18 years of age
- SCI, neurological disease with paralysis or multi trauma, all with lack of independency in position change in bed Hospitalized for primary rehabilitation in either the RMS or the MNB department
- Requires manual position change
- Medically approved for the participation by the patient's physician
- Able to consent to participate
- Psychically and cognitively able to properly answer the questionnaires

- Speaks/understands Norwegian language

Exclusion criteria

- Ongoing PI upon admission to the hospital
- External fixation, except use of neck-collar
- Body weight surpassing the mattress limits
- Pressure testing indicating a worse result than the set pressure limit
- The participant has a planned leave of absence during night time, during the test-period

Procedure

To secure safe use of the intervention mattress, a noise-test and a pressure assessment test of the mattresses has been performed in advance of the research project. A pressure limit is defined, based on current evidence based knowledge regarding pressure injury risk. If this limit is exceeded during the project period, the participant will be excluded from further testing, due to a potential increased risk of pressure injury development.

An Xsensor mat¹⁴ will be used in all pressure assessments. Written and oral information regarding the project will be given. The participants will give a written consent before inclusion. The regular care mattress, used as control in this trial, is considered one of the best pressure relieving mattresses available in Norway, and this mattress is the mattress of choice when the patient is admitted to the spinal cord unit for post-acute rehabilitation. Due to the randomized cross over design of the study, the start mattress will be chosen according to the randomization. The test-period will start with one of the mattresses for seven days, and then change back to the other mattress after seven days. This to secure a best possible objective comparison between the two mattresses. The study will be open labelled, because it will be impossible to mask the mattresses due to different designs. Ten participants will be included. Baseline data regarding gender, age, level and severity of the spinal injury, together with pressure injury associated dysfunction, like increased sweat, bladder and bowel incontinency, will be collected immediately after inclusion. Further, information of comorbidity previous to the injury or disease, including cardiovascular disease, embolisms or diabetes mellitus, will be registered. Pressure monitoring will be performed before start up, and validated questionnaires will be used in assessing pressure injury risk, pain and quality of life (QoL). After seven days use of the first mattress, new data will be collected, by means of validated forms regarding pressure injury occurrence, pain occurrence, noise from the mattress devices,

sleeping wellness and participant satisfaction. Custom made forms regarding resource use in the nursing staff, especially at night and in relation to position change, will be collected, together with data regarding physical strain in the staff. In-depth interviews will be performed on one participant and one nurse.

The participant will then change to the second mattress and use the mattress for seven days. Then a new data collection will be performed, similar to the questionnaires used in the first mattress. In-depth interviews will be performed in one participant and one nurse.

Collection of data and assessment instruments

At every shift during the project period, the nurses will check for pressure wounds, and mark identified pressure wounds on a pressure injury body-map. At every shift the nurses will also use a custom made form to register resources needed in each position changing of the patient, the number of times the position is changed, as well as the level of physical strain in the nurses. At the end of each of the two the test periods, the participants will register their QoL, bedrest comfort, sleep-wellness, pain and satisfaction in the test period.

One participant and one nurse will be asked to participate in in-depth interviews regarding experienced quality in use and in managing each of the mattresses.

Demographic data

Will be retrieved from the electronic patient record (EPR), and include gender, age, height and weight, injury-related information, time between the occurrence of the SCI as well as known injury-related risks, related to PI.

Primary Outcome Measure

Pressure Injury risk.

Assessment of PI risk will be performed via the Braden scale¹⁵. Every morning an evening any PI occurrence will be performed according to the NPIAP, 2019 Clinical Practice Guideline¹⁶, and any new mark/PI will be noted and rated on a severity scale ranging from 1 to 4. The location of the mark/PI will be marked on a body map chart, displaying the location of the mark/PI.

Secondary Outcome Measures

Health related quality of Life (HRQoL) regarding overall well-being, physical well-being and psychological well-being. Assessment will be performed using the spinal cord injury quality

of life basic data set (SCI QoL BDS)¹⁷. Assessment will be performed at baseline, at change of mattress and at end of study.

Sleep wellness assessment will be performed, using the Insomnia Severity Index (ISI)¹⁸.

Assessment will be performed at baseline, at change of mattress and at end of study.

Experienced pain when using the two mattresses will be assessed by using the Brief Pain Inventory (BPI)¹⁹. Assessment will be performed at baseline, change of mattress and at end of study.

Satisfaction in participants will be assessed using a custom-made Likert scale where 1 is completely dissatisfied and 5 is totally satisfied. Assessment will be performed at baseline, at change of mattress and at end of study.

Satisfaction in staff will be assessed as resource-use, counting the number of personnel needed, number of manual turnings required/level of required support during daytime/night-time, and physical strain in the nursing staff, using a custom made Likert scale where 1 is worst possible strain and 5 is no strain at all. Assessment will be performed at baseline, at change of mattress and at end of study.

A custom made semi-structured interview guide has been conducted, asking more details of the experienced quality in use and in managing the mattress.

Ethical considerations

The patient will be excluded from the study if risk of increased PI is apparent during the pre-test pressure mapping. The risk is determined by the pre-set pressure measurement limit.

The project will follow the national regulations regarding approval, collection and handling of sensitive data. Privacy regulations will be followed. The Tidewave mattress was approved by the Norwegian Medicines Agency (SLV) November 25th 2020, (NO918491775/0941-55297) and evaluated not to be included in the Ethical Committee's (REK) area of responsibility, January 15th 2021 (229188), and by the Patient Ombudsman at Sunnaas Rehabilitation hospital, September 16th 2021. Written and oral information will be given to all invited participants, and the participants have the right to withdraw from the project without giving any reason for the withdrawal.

Data processing

All data will be anonymized and stored at the hospital's encrypted data server. This is in line with the Norwegian privacy and data protection legislation. The data be available solely to individuals connected to the project. Any privacy information that can identify participants will be stored separately from the rest of the data. The letter of consent and the answers to the

questionnaires will be stored in a secure research cabinet. The keys to the cabinet are be stored securely. The data will be deleted 15 years after the conclusion of the study. Latest date of deletion is 1st of September 2037.

Consumer perspective

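### Under a two-sided 5% paired t-test, eight participants give about 0.70 power for the sleep comparison, not 0.8; ten completers are needed, so the two extra participants are not drop-out cover

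*Protocol*

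**What the plan says.** The Power calculation section of the protocol bases the sample size on the insomnia scale. Its inputs are:

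- **Effect:** "an improvement on 4.6 points on the ISS scale".
- **Variation:** "given the set assumptions regarding variation (SD = 4.5", taken from a published validation study of the scale.
- **Result:** "Based on this effect, a power of 0.8 and a significance level of 0.05, will need eight participants".
- **Enrolment:** "Thus, we include 10 participants to tolerate some" drop-outs. No drop-out rate is given.

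The section words its hypothesis directionally ("The hypothesis is that the sleep will improve when using the intervention mattress"). It names no test and no sidedness, and does not say whether 4.5 is the SD of paired differences or of single scores.

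Under Procedure, the design is a randomised crossover with seven days on each mattress, so each completer supplies one paired difference. The sleep scale is listed under Secondary Outcome Measures ("Sleep wellness assessment will be performed, using the Insomnia Severity Index"); the primary outcome is pressure injury risk.

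**The concern.** With fewer than about 20 pairs, a sample size from the normal distribution is noticeably too small for the t-test that would normally be used, because the SD must be estimated from few degrees of freedom (seven with eight pairs). The stated eight looked like such a figure.

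This matters because ten is justified as eight plus cover for losses. If ten is itself the requirement, there is no cover. The protocol provides for losses during the study. Under Procedure, on the pressure limit: "If this limit is exceeded during the project period, the participant will be excluded from further testing". Under Ethical considerations: "participants have the right to withdraw from the project without giving any reason". A participant who leaves before completing the second mattress gives no paired difference. A null sleep result from eight completers would then be read as coming from a comparison with a 20% type II error, when the figure would be about 30%.

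**Working it through.** **Inputs (Power calculation section).** Difference 4.6, SD 4.5, power 0.8, significance level 0.05. Assumption: 4.5 is the SD of the within-participant difference, which is the reading that leads to eight. Standardised difference d = 4.6/4.5 = 1.022.

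**Step 1. Reproduce the stated eight.** Two-sided normal formula for paired data:

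n = (z₀.₉₇₅ + z₀.₈₀)² / d² = (1.960 + 0.842)² × (4.5/4.6)² = 7.51, rounded up to 8.

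The formula for two parallel groups gives 16 per arm, so it is not the source.

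**Step 2. Power with the t distribution.** For n pairs, the test statistic is noncentral t with noncentrality d√n. At n = 8 this is 1.022 × √8 = 2.89, against a two-sided critical value of 2.365 on 7 degrees of freedom (the normal value is 1.960). Power by number of completers:

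| Test | n = 8 | n = 9 | n = 10 |
|---|---|---|---|
| Two-sided 5%, df = n − 1 | 0.70 | 0.77 | 0.82 |
| Two-sided 5%, period term, df = n − 2 | 0.68 | 0.75 | 0.81 |
| One-sided 5%, df = n − 1 | 0.83 | 0.87 | 0.91 |
| One-sided 5%, period term, df = n − 2 | 0.82 | 0.87 | 0.90 |

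On the two-sided rows, ten is the first number to reach 0.8. On the one-sided row without a period term, seven gives 0.77, so eight is the first. A simulation of 400,000 runs for the first row gave 0.701, 0.767 and 0.819.

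**Step 3. What would rescue eight on a two-sided test.** Eight completers reach 0.80 only if the SD of the difference is at most 3.98, or if the true difference is at least 5.2 points with the SD at 4.5.

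**Step 4. If 4.5 is a between-person SD (assumption).** Then the SD of the difference is 4.5 × √(2(1 − ρ)), where ρ is the correlation between a participant's two scores. The protocol gives no ρ, so a range is shown (two-sided, df = n − 1):

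| ρ | SD of difference | Power, n = 8 | Power, n = 10 | Completers for 0.8 |
|---|---|---|---|---|
| 0.3 | 5.32 | 0.56 | 0.68 | 13 |
| 0.5 | 4.50 | 0.70 | 0.82 | 10 |
| 0.7 | 3.49 | 0.89 | 0.96 | 7 |

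Eight is enough from ρ = 1 − 3.98²/(2 × 4.5²) = 0.61 upwards.

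**The case against.** The strongest reply is that the protocol names no test, sidedness or SD type, so the 0.70 rests on choices made by the reader, and some of these could sit in an analysis plan that is not at hand. The hypothesis is directional, and a one-sided 5% paired t-test makes eight exactly right and the drop-out sentence true. A between-person SD with a high enough correlation also makes eight sufficient. On this view the paragraph is ambiguous rather than wrong.

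It can be added that the effect is modest: sleep is secondary, ten completers still give 0.82, one loss costs three points against 0.8, and only some drop-outs are promised to be covered. Part of the pressure-limit exclusions may also fall at the pre-test mapping, before a participant counts among the ten, and the right to withdraw is a standard statement rather than a forecast.

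These points limit the finding but do not remove it. A directional hypothesis is not a declaration of a one-sided test, and an unqualified 0.05 is ordinarily read as two-sided. No correlation is stated, and a lower one would make matters worse. The protocol itself fixes eight as the requirement and ten as cover, so this is not a detail left for later. What stands of the objection is that the shortfall is conditional on the two-sided reading and on 4.5 being the SD of the difference.

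**Conclusion.** The concern holds. On the usual reading, eight completers give 0.70 power rather than 0.8 (0.68 with a period term), and the margin of two is not a drop-out allowance at 0.8 power. One loss from ten takes power to 0.77, two to 0.70.

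This assumes a two-sided 5% paired t-test and an SD of the within-participant difference of 4.5. It reverses if a one-sided 5% test was intended, and it shifts in either direction if 4.5 is a between-person SD. The protocol declares neither. The finding is confined to the sleep comparison; the section says nothing about power for pressure injury risk. It should be corrected, but it does not call for a larger trial.

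**What to change.** Restate the paragraph using the t distribution. Suggested wording: *For the Insomnia Severity Index (secondary outcome), with a within-participant difference of 4.6, an assumed SD of the difference of 4.5 and a two-sided 5% paired t-test, 10 completers give 82% power, 9 give 77% and 8 give 70%.* Remove the statement that ten allows for drop-outs.

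If a one-sided 5% test was intended, declare it, state that 8 completers give 83%, and use the same one-sided test in the analysis. The drop-out sentence can then stay.

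In either case, say whether 4.5 is the SD of paired differences or a between-person SD. If it is between-person, state the assumed correlation and recompute the figures.

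The cost is one paragraph of wording and, on the two-sided test, a less favourable stated power after drop-out. No participants need to be added.

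### Does the protocol contradict itself on whether a person over the pressure limit counts among the ten participants?

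*Protocol*

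**What the plan says.** The Exclusion criteria list, as a reason not to enrol someone, "Pressure testing indicating a worse result than the set pressure limit". Ethical considerations ties the same limit to the mapping done beforehand: "The patient will be excluded from the study if risk of increased PI is apparent during the pre-test pressure mapping".

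Procedure gives a further rule, justified by the risk of pressure injury: "If this limit is exceeded during the project period, the participant will be excluded from further testing". The same section says that baseline data on sex, age, injury and related dysfunction "will be collected immediately after inclusion", and continues: "Pressure monitoring will be performed before start up, and validated questionnaires will be used in assessing pressure injury risk". Before start-up is the only time the protocol names for a pressure measurement in participants.

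On numbers, Power calculation states that the trial "will need eight participants, given the set assumptions regarding variation" and that "we include 10 participants to tolerate some" drop-outs.

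**The concern.** One threshold has two consequences. As an exclusion criterion, it means a person over it never enters the trial. Under the Procedure rule, a person over it has already entered and is lost. Procedure mentions the mapping after the inclusion of ten and after the baseline data, and no later pressure measurement has a stated time. A reader can therefore conclude that both rules act on the same single mapping, that an entry criterion is measured after entry, and that the protocol gives two answers on whether such a person is one of the ten.

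In so small a trial that would count. The allowance is two people. If people who fail the mapping used it up before anyone dropped out, the number completing could fall below eight. Bias is not at issue, because a loss before either mattress is used does not distort the within-person comparison.

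**Working it through.** **1. The rules side by side**

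| Protocol section | When the limit is applied | Who is affected | Consequence |
|---|---|---|---|
| Exclusion criteria | At selection | A candidate | Not included |
| Ethical considerations | At the mapping before testing | A patient | Excluded from the study |
| Procedure | During the project period | A participant | No further testing |

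The first two rows describe one check. The third describes a later event. A person over the limit at the first mapping is not one of the ten. A person who passes and exceeds it later is one of the ten and stops. Each case has one answer, and staff can follow all three statements. Using one threshold both for eligibility and for discontinuation is ordinary design.

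**2. What the project period means**

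The conflict needs this term to cover the mapping before the start. The protocol's other relevant use points the other way: in Collection of data and assessment instruments, it is the time over which nurses check the skin at every shift and record position changes. That is time on the mattresses. The Procedure rule also bars further testing, which presupposes that testing has begun.

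**3. Whether the entry test is placed after entry**

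This inference rests on sentence order alone, and Procedure is not written in time order. The sentence on including ten participants comes after the randomised start mattress, the two seven-day periods, the switch and the open-label design have been described. Its position cannot date the mapping. The wording that does give a time, "Pressure monitoring will be performed before start up", fits mapping before inclusion, which the exclusion criterion requires.

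**4. The numbers**

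Inputs from Power calculation: difference 4.6 points, SD 4.5, power 0.80, significance level 0.05. The protocol does not say whether the test is two-sided or what the SD refers to; I take two-sided and the SD of paired differences.

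- Normal approximation: n = (4.5 × (1.960 + 0.842) / 4.6)² = 7.51, rounded up to 8. This reproduces the protocol's figure.
- Allowance: 10 − 8 = 2 people, or 8 / (1 − 0.20) = 10.
- Paired t-test power, with standardised difference 4.6 / 4.5 = 1.022 and noncentrality 1.022 × √n on n − 1 degrees of freedom:

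| Completing | Power |
|---|---|
| 10 | 0.82 |
| 9 | 0.77 |
| 8 | 0.70 |
| 7 | 0.62 |

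The table gives the cost of losing a participant for any reason. It is not specific to the pressure limit, and the protocol gives no rate at which the limit is exceeded. Someone stopped under the Procedure rule is a drop-out of the kind the two extra places cover; someone screened out uses none of them.

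**The case for a change.** The strongest reply is that two rules acting at different times need two measurements, and only one has a stated time. The assessments at the end of each mattress week are described as forms and questionnaires, and the checks at every shift are skin inspections. Without a dated measurement after the start, the only dated trigger for the Procedure rule is the mapping before start-up, which the exclusion criterion also uses. The two rules would then meet at one measurement and give different counts.

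Part of this stands. The protocol does not schedule a pressure measurement after the start, does not name the mattress that is mapped, and does not say in so many words that mapping comes before inclusion. But a rule without a scheduled measurement is incomplete; it does not become a rule about an earlier time. The stop is expressly limited to the project period, and the lack of a date does not move it to before the start. Nor does the gap change the count at the first mapping, where the Exclusion criteria and Ethical considerations both say that the person is out. Staff could fill in the missing detail sensibly without departing from anything written.

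**Conclusion.** The concern does not hold. The entry exclusion and the later stop act at different times, and together they give one answer to who counts among the ten: people over the limit at the mapping beforehand do not, and people who exceed it later do. The eight needed and the ten included are unaffected, and no bias arises from this point.

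The conclusion rests on two readings: that the project period means the time on the mattresses, as in the data-collection section, and that the mapping before start-up is the one the exclusion criterion relies on. Both are the more natural readings, and nothing in the protocol contradicts them. The unstated timing details are small omissions that alter no figure or conclusion. How stopped participants are handled in the analysis may be left to the statistical analysis plan, which is not available here.

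### Does switching directly between two seven-day mattress periods let the first mattress leak into the second questionnaire score?

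*Protocol*

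**What the plan says.** The design is a randomised, open-label crossover with ten participants and 14 days each, seven per mattress (Selection of participants; Procedure). The switch is direct: "The test-period will start with one of the mattresses for seven days, and then change back to the other mattress after seven days". Since 7 + 7 = 14, no days are left for a washout.

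The Procedure section places the first data collection after seven days on the first mattress; the participant then moves to the second. For quality of life, sleep and pain, the Secondary Outcome Measures section gives only the timing: "Assessment will be performed at baseline, at change of mattress and at end of study". The section on data collection and assessment instruments adds that, at the close of each of the two periods, participants rate their quality of life, comfort, sleep, pain and satisfaction for that period.

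On the mattress used before the study, the Procedure section says of the control that "this mattress is the mattress of choice when the patient is admitted to the spinal cord unit for post-acute rehabilitation". On the size of the sleep effect, the Power calculation section says that "the expectation is a low improvement, due to the low period of time the intervention mattress will be in use". It plans for "an improvement on 4.6 points on the ISS scale", "given the set assumptions regarding variation (SD = 4.5", and states that "a power of 0.8 and a significance level of 0.05, will need eight participants"; then "we include 10 participants to tolerate some drop- outs".

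**The concern.** A crossover gains its precision from comparing each participant with themselves, so anything that mixes the two conditions in one score erodes the contrast. Two routes seem open here.

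- **True carry-over.** The sponsor calls seven days short for a sleep benefit. If the benefit is slow to build, it might also be slow to fade, and a control week after the new mattress would then look better than it should. Participants probably arrive from weeks on the control mattress, so the leakage would run mainly in one sequence.
- **Recall.** No reference period is stated for any single instrument. A form that looks back more than seven days would, on day 14, cover nights on the first mattress.

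Both routes would pull the sleep contrast towards zero, and the sample size allows for neither.

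**Working it through.** **Inputs from the Power calculation section.** Difference 4.6 points, SD 4.5, power 0.80, significance level 0.05, stated need 8, planned 10. The protocol does not say whether 4.5 is the SD of a score or of a within-participant difference, nor whether the test is two-sided. The difference and two sides are assumed here.

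**The plan's own figure.** The paired normal approximation gives n = ((1.960 + 0.842) × 4.5 / 4.6)² = 7.51, rounded up to 8. The stated figure reproduces. A two-sided paired t-test would need 10, and with 10 its power is 0.82.

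**Route 1, true carry-over.** Assume that the control is the pre-study mattress, that the sequences split 5:5, and that a fraction L of the effect persists at the end of a following control week. The contrast is (1 − L) × 4.6 when the new mattress comes first and 4.6 when it comes second. The mean is (1 − L/2) × 4.6.

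| L | Contrast | Power, n = 10 |
|---|---|---|
| 0 | 4.60 | 0.82 |
| 0.25 | 4.03 | 0.71 |
| 0.50 | 3.45 | 0.58 |

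If instead a share s of the second score reflects the first mattress in both sequences, the contrast is (1 − s) × 4.6. Shares of 0.10, 0.25 and 0.50 give 4.14, 3.45 and 2.30 points, with power 0.74, 0.58 and 0.30.

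**Route 2, recall window of w days (7 to 14), each night weighted equally.** With the new mattress first, the day-7 score contains 7/w of the effect and the day-14 control score contains (w − 7)/w, so the contrast is (14 − w)/w. With the new mattress second, it is 7/w. The mean is (21 − w)/(2w).

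| w | Share of effect left | Contrast | Power, n = 10 |
|---|---|---|---|
| 7 | 1 | 4.60 | 0.82 |
| 10 | 11/20 = 0.55 | 2.53 | 0.36 |
| 14 | 7/28 = 0.25 | 1.15 | 0.11 |

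**Which row applies.** The arithmetic is right, but the protocol supplies no value for L or s. For w, the only indication is the data-collection text, which asks at the end of each period about that period. That is w = 7, the row with no loss.

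**Does slow onset imply persistence?** The power text says only that a short exposure is expected to yield a small benefit. It does not say how quickly that benefit disappears. Each score is taken after seven days on the current mattress, so the earlier nights of each period already act as a lead-in.

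**The case for a change.** The strongest case for a change is that recall is a matter of data collection: once the forms are answered, no analysis plan can separate the nights. The term for the test period is also used inconsistently. The Procedure section applies it to the whole 14-day sequence, and the data-collection section to each seven-day period. The same instruments are given at baseline, before any period has begun, so nothing shows that their printed wording is limited to seven nights. The remedy would be a single line on existing forms.

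Part of this stands. The term is used loosely, and no window is stated instrument by instrument. But the sentence that governs the participant forms speaks of two periods and asks about each at its end, and the pain outcome is described by reference to use of the mattresses. Completing the first form before the switch is already the stated order. A line on the form would write down that reading without altering the comparison, and would cost some comparability with published scores. It could not remove true carry-over. Nor is a washout in the ordinary sense available, since a patient must always lie on some mattress.

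The one-sided direction is also less certain than it looks: the control is described as the usual choice, not as the mattress every participant had used.

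**Conclusion.** The back-to-back switch is real, and mixing of the two mattresses would shrink the contrast. No change follows. Under the reading that the data-collection section supports, recall costs nothing: the contrast stays at 4.6 points and power with 10 stays at 0.82 (two-sided paired t, 4.5 taken as the SD of the difference). The lower figures, down to 0.58 for one-sided carry-over and 0.11 for recall, need a persistence of 25–50% or a window of 10–14 days that the protocol neither states nor implies. True carry-over cannot be ruled out from the document, but its size cannot be derived either.

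The figures concern the sleep score, which is a secondary outcome although it sets the sample size. They do not bear on the primary outcome, pressure injury risk, or on the nurses' shift-by-shift records, which do not depend on participants' recall. Two direct seven-day periods are a fair trade-off in an inpatient stay, and the loose term is a wording matter that those running the trial would settle sensibly.
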